5.3.6. Other Efficacy Endpoints

In addition to the primary and key confirmatory secondary endpoints, other efficacy analyses related to reduction of signs and symptoms and physical function, skin disease, nail psoriasis, joint structural damage, and health related quality of life will be analyzed. These endpoints are NOT adjusted for multiplicity, and any p-values calculated will be considered nominal.

Treatment comparisons will ONLY be performed up to the Week 24 visit. Subsequent visits through Week 156 will be limited to descriptive summaries or model based estimates by study intervention.

5.3.6.1. Estimands

The estimand is composed of 5 components: Population, treatment, variable, intercurrent events, and population level summary. Of these, population, variable, and population level summary vary across the different endpoints, while treatment and intercurrent events are constant. For all endpoints, the treatments are placebo and the 2 guselkumab dose groups. Additionally, the definition of intercurrent events are defined below.

Adjusted Composite Estimand (for non-radiographic endpoints)

This estimand was previously defined for the primary analysis of ACR 20 response at Week 24 in Section 5.3.4.2. The ICEs are generalized across endpoints and for all efficacy visits below:

- **Intercurrent Events:**

1. Discontinued study intervention injections due to any reason **except** due to Natural Disaster or Major Disruption.
2. Initiated or increased the dose of non-biologic DMARDs (MTX, SSZ, HCQ, LEF) or oral corticosteroids over baseline for PsA.
3. Initiated protocol prohibited medications/therapies for PsA.
4. Discontinued study intervention injections due to Natural Disaster or Major Disruption.
5. Severe treatment non-compliance due to Natural Disaster or Major Disruption. This is defined for a given visit, when the total number of doses of study intervention missed due to Natural Disaster or Major Disruption exceeds 30% of the total protocol defined doses from Week 0 up to and including that visit. For Week 20, this amounts to ≥ 2 dose missed:

6. Decided to NOT enter the LTE due to lack of efficacy OR adverse event of worsening of PsA (only relevant after Week 48).

*Note that in the context of ICEs and missing data, the following are defined:

1. **Natural Disaster:** site closure, site access restrictions, or lockdowns caused by COVID-19.
2. **Major Disruption:** the disruption involving Ukraine and neighboring countries/territories beginning February 24, 2022

Treatment Policy Estimand (for non-radiographic endpoints)

This estimand was previously defined for the primary endpoint of ACR 20 response at Week 24 in Section 5.3.4.2 and for the change from baseline in modified vdH-S score at Week 24 in Section 5.3.5.1.2. The ICEs and their handling are generalized across endpoints and for all efficacy visits below:

- **Intercurrent Events:** the definition of the 6 categories of ICE are the same as the generalized Adjusted Composite Estimand in this Section.

Adjusted Treatment Policy Estimand (for radiographic endpoints only)

This estimand was previously defined for the main analysis of change from baseline to Week 24 in modified vdH-S score in Section 5.3.5.1.2. The ICEs are generalized across endpoints and for all efficacy visits below:

- **Intercurrent Events:** the definition of the 6 categories of ICE are the same as the generalized Adjusted Composite Estimand in this Section.

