### **6.8.6. Topical Therapy and Ultraviolet B Light**

Concurrent use of topical medications/treatments for psoriasis (eg, topical or intralesional corticosteroids, keratolytics (with the exception of salicylic acid shampoos, which are allowed throughout the study), coal tar (with the exception of coal tar shampoos, which are allowed throughout the study), anthralin, vitamin D3 analogues, or topical tacrolimus, and retinoids) are not permitted through Week 24.

Use of salicylic acid- and tar-containing shampoos is not permitted on the morning prior to a study visit; non-medicated shampoos may be used on the day of a study visit.

Low-potency topical corticosteroids may be used on the face and groin only. Low and mid-potency topical or intralesional corticosteroids (Class III-VII) may be used after Week 24 for psoriasis. High and ultra-high potency corticosteroids (Class I and II) are prohibited through Week 48.

Phototherapy including UVB or tanning beds are not permitted during the study through Week 168. Participants should be encouraged to avoid prolonged sun exposure during the study.

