5.3.6.3.4. Method of Analysis

In general, the same methods of analysis for the Other Efficacy endpoints related to reduction of signs and symptoms and physical function in Section 5.3.6.2.10 will also be used for those related to skin disease.

Table 11 summarizes the analyses for supportive efficacy endpoints related to skin disease, the methods for analyses, and the data handling rules used.

Table 11: Summary of Estimands, Analysis Sets, Data Handling Rules, and Analysis Methods for Endpoints of Skin Disease

	Endpoint	Analysis Set	Missing Data Rules	Analysis Methods
ENDPOINTS BY VISIT THROUGH WEEK 24 AT WEEK-24 DBL, ADJUSTED COMPOSITE ESTIMAND				
1	Change from baseline in PASI score	mFAS with $\geq 3\%$ BSA and IGA ≥ 2 at baseline	-	
 • Summarized descriptively • LS mean (95% CI) for each intervention group, LS mean difference (95% CI) and p-values for differences between groups based on MMRM
2	Percent change from baseline in PASI score	mFAS with $\geq 3\%$ BSA and IGA ≥ 2 at baseline	-	
 • Summarized descriptively • LS mean (95% CI) for each intervention group, LS mean difference (95% CI) and p-values for differences between groups based on MMRM
3	Proportions of participants with PASI $\geq 75\%$, $\geq 90\%$, $\geq 100\%$ improvement	mFAS with $\geq 3\%$ BSA and IGA ≥ 2 at baseline	NRI for MAR not due to Natural Disaster or Major Disruption	
 • Summarized descriptively Response rates, and treatment difference in response rates and 95% CI and pvalue, based on GLMM
4	Proportion of participants with both PASI $\geq 75\%$ improvement and ACR 20 response	mFAS with $\geq 3\%$ BSA and IGA ≥ 2 at baseline	NRI for MAR not due to Natural Disaster or Major Disruption	
 • Summarized descriptively • Response rates, and treatment difference in response rates and 95% CI and pvalue, based on GLMM

Table 11: Summary of Estimands, Analysis Sets, Data Handling Rules, and Analysis Methods for Endpoints of Skin Disease

	Endpoint	Analysis Set	Missing Data Rules	Analysis Methods
5	Proportion of participants with both PASI $\geq 75\%$ improvement and modified PsARC response	mFAS with $\geq 3\%$ BSA and IGA ≥ 2 at baseline	NRI for MAR not due to Natural Disaster or Major Disruption	
 Summarized descriptively Response rates, and treatment difference in response rates and 95% CI and pvalue, based on GLMM

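### For skin and nail endpoints, the intercurrent-event list counts prohibited therapy and DMARD or oral-steroid increases only when given for PsA, so banned topical or UVB treatment for psoriasis need not make a participant a non-responder

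*SAP*

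**What the plan says.** SAP 5.3.6.1 says of the estimands for Other Efficacy endpoints that "population, variable, and population level summary vary across the different endpoints, while treatment and intercurrent events are constant". Two entries on the common list matter here. ICE 2 is "Initiated or increased the dose of non-biologic DMARDs (MTX, SSZ, HCQ, LEF) or oral corticosteroids over baseline for PsA". ICE 3 is "Initiated protocol prohibited medications/therapies for PsA". SAP Appendix 14 repeats both.

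For skin endpoints, SAP 5.3.6.3.4 states that in general "the same methods of analysis for the Other Efficacy endpoints related to reduction of signs and symptoms and physical function" apply. SAP 5.3.6.4.3 does the same for nails. Under SAP 5.3.6.2.10, a participant who meets ICE 1, 2, 3 or 6 is a treatment failure from then to the final efficacy visit: a non-responder on binary endpoints and zero change on continuous ones. Tables 11 and 12 add no rule for psoriasis therapy.

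Protocol 6.8.6 bars "Concurrent use of topical medications/treatments for psoriasis" through Week 24, with exceptions for certain shampoos and for low-potency steroid on the face and groin. Class I and II topical steroids are barred through Week 48. On light treatment it says: "Phototherapy including UVB or tanning beds are not permitted during the study through Week 168". Low- and mid-potency topical steroids become permitted after Week 24.

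**The concern.** The composite strategy treats a switch to other active treatment as failure. For a skin or nail endpoint, the treatments most likely to distort the score are those aimed at the skin. Protocol exclusion criteria 9 and 10 say so: they exclude recent phototherapy and topical treatments because these could affect psoriasis evaluations. Yet the list is worded around the joint indication, and skin-directed therapy can fall outside it.

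At stake are the PASI, IGA, DLQI, mNAPSI and PGA-F results and the combined PASI 75 endpoints. Tables 11 and 12 report between-group differences, confidence intervals and p-values for these through Week 24, and descriptive or model-based rates by arm afterwards.

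**Working it through.** No figure in the plan depends on this point, so there is nothing to reproduce. The check is a reading of the text, followed by an illustration of size.

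**Does the wording for PsA cover psoriasis?** It cannot be assumed to. Protocol 6.8.5 names PsA and psoriasis separately when it means both. SAP Appendix 8 lists prior therapies for PsA and for psoriasis in separate rows, and topicals and UVB appear only in the psoriasis row.

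**Does another rule catch the case?**
- ICE 1 (stopping injections): Protocol 6.8.6.1 makes stopping mandatory for systemic psoriasis therapy, including psoralen with UVA, but exempts the Table 3 drugs. For prohibited therapy in general, Protocol 7.1 asks only that the medical monitor be told so that discontinuation can be considered. A topical agent or UVB therefore does not trigger ICE 1 automatically.
- ICE 2: a Table 3 DMARD or an oral steroid started or raised for psoriasis falls outside the wording and outside mandatory discontinuation.
- Treatment Policy analysis: it ignores ICEs and uses observed data.
- Per-protocol set: SAP 4.5 names it for selected endpoints, but it is specified only for ACR 20 (SAP 5.3.4.4, Sensitivity Analysis 5).

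**Size.** Let r be the share of an arm that uses uncounted psoriasis therapy before Week 24, stays on injections and meets no other ICE. Let q be the share of those who reach the threshold, and p the response rate among the rest.
- Rate as written: (1 − r)p + rq
- Rate if such use is failure: (1 − r)p
- Inflation in that arm: rq
- Understatement of the difference, with the same q in both arms: q(r_placebo − r_guselkumab)

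The documents give no values for r, q or p, so all inputs below are assumptions.

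| r placebo | r guselkumab | q | Inflation, placebo | Inflation, guselkumab | Difference understated by |
|---|---|---|---|---|---|
| 3% | 1% | 0.5 | 1.5 points | 0.5 | 1.0 |
| 10% | 1% | 0.5 | 5.0 | 0.5 | 4.5 |
| 5% | 1% | 0.3 | 1.5 | 0.3 | 1.2 |
| 15% | 3% | 1.0 | 15.0 | 3.0 | 12.0 |
| 5% | 5% | 0.6 | 3.0 | 3.0 | 0 |

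One case in full: take p = 10% on placebo and 75% on guselkumab, r = 5% and 1%, q = 0.6. With such use as failure, the rates are 0.95 × 10% = 9.5% and 0.99 × 75% = 74.25%, a difference of 64.75 points. As written, they are 9.5 + 3.0 = 12.5% and 74.25 + 0.6 = 74.85%, a difference of 62.35 points. The shift is 2.4 points, which equals 0.6 × (5 − 1).

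The shift does not depend on p. If use were higher on guselkumab, its sign would reverse.

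**The case against.** **The rule might seem to fail the wrong patients.** A reader might infer this because a participant who raises methotrexate for joint pain becomes a PASI non-responder. The documents do not support that reading. Exclusion criterion 9 and Protocol 6.8.6.1 carve the Table 3 drugs out of a class of systemic treatments that affect psoriasis, so counting a methotrexate increase as failure on PASI is coherent. The fault is an omission, not a reversed rule.

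**ICE 1 may catch some cases.** The sponsor must be told of any prohibited therapy (Protocol 6.8), discontinuation may follow, and Protocol 7.1 requires stopping for participants who cannot comply with the protocol. This stands and narrows the gap, but none of these routes is automatic for a topical agent or UVB.

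**Redaction.** The skin and nail endpoint definitions are partly blacked out. SAP Appendix 10 does handle joint injections at the level of the endpoint definition, so a comparable skin rule could exist unseen. What can be read is the ICE list, the strategies, Tables 11 and 12 and Appendix 14, and none of them contains one.

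**Low stakes.** SAP 5.3.6 places these endpoints outside multiplicity control with nominal p-values. If use is higher on placebo, the contrast is biased against guselkumab. Both points stand and limit the priority.

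**Conclusion.** The gap is real on the readable text. Prohibited topical or UVB therapy, or a DMARD or oral-steroid increase, given for psoriasis meets no automatic ICE. A participant who stays on injections, meets no other ICE and reaches the threshold counts as a responder on a skin or nail endpoint.

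Absolute response is inflated by rq in any arm where this occurs. A reader might infer that the Week 24 treatment difference is necessarily understated. That needs higher use on placebo, which is plausible because skin disease there is not treated with guselkumab, but no document reports it. The 1 to 4.5 points rest wholly on assumed use of 3% to 10% against 1% with half responding; equal use gives zero. For change and percent-change endpoints, the observed score likewise replaces zero change, but no size can be given.

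The primary ACR 20 analysis and the vdH-S endpoint are unaffected, and no confirmatory claim depends on this point. It should be corrected because the repair is small, but it does not threaten the trial's main conclusions.

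**What to change.** In SAP 5.3.6.1 and Appendix 14, for the endpoints in 5.3.6.3 and 5.3.6.4 only (including the combined PASI 75 endpoints):

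1. Let ICE 2 and ICE 3 apply when the therapy is given for PsA or psoriasis.
2. State that ICE 3 includes topical agents and phototherapy that Protocol 6.8.6 prohibits at the time of use. Score these as treatment failure through Week 24.
3. For later descriptive visits, state that failure from a topical agent does not carry forward once the protocol permits that class. Without this, SAP 5.3.6.2.10 would make one use of a mid-potency steroid before Week 24 a failure through Week 156, although that class is permitted after Week 24.

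Leave ACR 20 and the joint-only endpoints as they are. If the relevant database lock has passed, run this as a sensitivity analysis beside the planned one.

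Cost: SAP wording and some programming. Protocol 6.8 already requires therapy type, period, dosage, route and indication to be recorded, so no new collection is needed for the indication. Topical steroids would have to be classed by potency, and exempt face or groin use identified, before unblinding where possible. The result is a few more treatment failures and some departure from a single constant ICE list.

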**Footnotes:**

- a: Through Week 156 study visits will have a visit window of  $\pm 7$  days; Week 168 visit or the final safety visit (12 weeks after the last dose in participants who discontinued study treatment) will have a visit window of  $\pm 14$  days.
- b: This final safety visit is for participants who have entered long term extension.
- c: PSA evaluations for arthritis include joint assessments (swollen and tender joint counts), patient's assessment of pain, patient's global assessment of disease activity (arthritis), and physician's global assessment of disease activity on VAS. These procedures should be performed prior to study intervention administration at each visit, as applicable.
- d: All participant questionnaires should be performed before any other tests, procedures, or evaluations on the day of the visit.
- e: Single radiographs of the hands (posteroanterior) and feet (anteroposterior) should be performed within  $\pm 2$  weeks of the Week 48, 96 and 156 visits. For participants who permanently discontinue study intervention after Week 24 but prior to Week 156, and participation at any time during the study radiographs of hands and feet should be performed at the time of discontinuation of study intervention or as soon as possible unless another set of radiographs has been obtained within the past 6 weeks.
- f: Vital signs include blood pressure and heart rate.
- g: TB evaluation must include specific questions about symptoms of TB or known occupational or other personal exposure to individuals with active TB.
- h: Laboratory tests are listed in Section 8.2.5.
- i: Study intervention will be administered SC q4w through Week 156. At any time point, where there is no study visit, participants have the option to come to the site for study intervention administration or may self-administer or can have another health care provider or a caregiver administer at home.
- j: All blood samples must be collected before study intervention administration at visits when study intervention administration is scheduled. Blood collected from one venipuncture will be divided into multiple aliquots of serum for the measurement of guselkumab concentration, antibodies to guselkumab, and a back-up sample.
- k: This represents the same visit as the Week 48 (final [core study] efficacy visit) in Table 1. Study procedures should only be performed once.
- l: PBMCs will be collected at sites where logistically feasible.

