- **NP:** [(CRP<5.7 and ERN<=5) OR (CRP<5.7 and 5<ERN<16 and COR=Yes)] AND (R_DIFF_ERN = No)
- **LMP:** [Other] AND (R_DIFF_ERN = No)

With the abbreviations standing for:

COR = the participant's baseline oral corticosteroid use

ERN = the participant's baseline number of joints with erosion

R_DIFF_ERN = (Yes/No) if the absolute reader difference for number of joints with erosions at baseline was >8

CRP = the participant's most recent screening CRP Level in mg/dL

Group I (n=350)

Participants will receive SC guselkumab 100 mg at Weeks 0, 4, 12, 20, 28, 36 and 44 and placebo at Weeks 8, 16, 24, 32, 40 and 48 to maintain the blind.

Group II (n = 250)

Participants will receive SC guselkumab 100 mg at Weeks 0, 4, 8, 12, 16, 20, 24, 28, 32, 36, 40, 44 and 48.

Group III (n=350)

[figure not shown]
Participants will receive SC placebo at Weeks 0, 4, 8, 12, 16 and 20, and will cross over at Week 24 to receive SC guselkumab 100 mg at Weeks 24, 28, 32, 36, 40, 44 and 48.

At Week 16, all participants in Groups I II and III with < 20% improvement from baseline in both tender and swollen joint counts will qualify for early escape (EE) and will be allowed to initiate or increase the dose of one of the permitted concomitant medications up to the maximum allowed dose as specified in [Table 2](#), as selected by the investigator.

The core study lasts from Screening to Week 48. At Week 48, participants who have not discontinued will be eligible to enter a long-term extension (LTE) for a period of up to approximately two years (ie, Week 48 through Week 156) where they will continue on the same treatment regimen.

Database locks (DBLs) are scheduled at Weeks 24, 48, 96 and end of study (Week 168). The first DBL will occur when all randomized participants have either completed the Week 24 assessments or terminated study participation prior to the Week 24 visit (referred to as Week-24 DBL). The second DBL will occur when all randomized participants have either completed the Week 48 assessments or terminated study participation prior to the Week 48 visit (referred to as Week-48 DBL). The third DBL will occur when all randomized participants have either completed the Week 96 assessments or terminated study participation prior to the Week 96 visit (referred to as Week-96 DBL). The fourth and final DBL will occur when all randomized participants have either completed their final safety visit or have terminated study participation.

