5.3.4.2. Estimand

Adjusted Composite Estimand (Primary)

The **primary** analysis for the primary endpoint will be based on the Adjusted Composite Estimand. This estimand is defined by the 5 components:

- **Population:** Participants with active PsA who are biologic naïve
- **Treatment:**
 - Placebo
 - Guselkumab
- **Variable:** ACR20 composite binary response variable at Week 24, where a responder is defined as a participant who achieves ACR20 response at Week 24 and does not experience ICE categories 1 to 3 prior to that time, in the hypothetical situation where Natural Disaster or Major Disruption and associated ICE categories 4 and 5 did not occur.
- **Intercurrent Events:**
 1. Discontinued study intervention injections due to any reason **except** due to Natural Disaster or Major Disruption.
 2. Initiated or increased the dose of non-biologic DMARDs (MTX, SSZ, HCQ, LEF) or oral corticosteroids over baseline for PsA.
 3. Initiated protocol prohibited medications/therapies for PsA.
 4. Discontinued study intervention injections due to Natural Disaster or Major Disruption.
 5. Severe treatment non-compliance due to Natural Disaster or Major Disruption, defined as ≥ 2 doses of study intervention missed due to Natural Disaster or Major Disruption.
- **Population level summary:** difference in proportion of responders (as per definition of **Variable** above) between guselkumab group and placebo group.

*Note that in the context of ICEs and missing data, the following are defined:

1. **Natural Disaster:** site closure, site access restrictions, or lockdowns caused by COVID-19.
2. **Major Disruption:** the disruption involving Ukraine and neighboring countries/territories beginning February 24, 2022

This estimand examines the difference in proportion of participants who achieve ACR20 response after 24 weeks without increasing/initiating select background PsA medications or discontinuing study intervention (for reasons not due to Natural Disaster or Major Disruption) prior to that point and in the hypothetical scenario where the Natural Disaster or Major Disruptions did not occur,

between each guselkumab group individually versus placebo, amongst participants with active PsA who are biologic naïve.

Additional supplementary analyses will be conducted on the primary endpoint using the Treatment Policy Estimand, aiming to achieve a robust treatment effect for regulatory decision making:

Treatment Policy Estimand (*Supplementary*)

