5.3.6.2.10. Method of Analysis

In general, descriptive statistics, such as mean, standard deviation (SD), median, inter quartile (IQ) range, minimum, and maximum for continuous variables, and counts and percentages for discrete variables will be used to summarize most data.

The **main analysis** for Other Efficacy endpoints related to reduction of signs and symptoms and physical function will be conducted using the Adjusted Composite Estimand. The ICE Strategy handling rules for the estimand will be applied first, after which the data handling rules for missing data will be applied. Specifically:

ICE Strategies for Adjusted Composite Estimand

For the Adjusted Composite Estimand, ICE categories 1, 2, 3, and 6 are incorporated as part of the endpoint using the composite strategy. This estimand acknowledges that a participant increasing their background PsA medications, electing to discontinue study intervention for reasons other than Natural Disaster or Major Disruption, or not entering the LTE due to lack of efficacy or worsening of PsA is an unfavorable outcome where participants who meet them prior to the visit will be considered as treatment failures at that visit and subsequently through the final efficacy visit. Participants meeting TF are considered non-responders for binary response endpoints, and to have no improvement (change from baseline = 0) for continuous endpoints, regardless of observed data.

This estimand also employs the hypothetical strategy. Primarily, regarding significant unplanned changes to study conduct as a result of Natural Disaster or Major Disruption. This estimand seeks to estimate the treatment effect of study intervention as if Natural Disaster or Major Disruption, as well as ICEs directly resulting from them, did not occur. Thus, for ICE category 4 all observed data after meeting the ICE through end of study will not be used and will be assumed to be MAR. For ICE category 5, observed data at the visit immediately subsequent to meeting the ICE will not be used and will be assumed to be MAR.

For participants experiencing multiple ICEs, an ICE in categories 1, 2, 3, and 6 (ie, using the composite strategy) will supersede an ICE in categories 4 or 5 (ie, using the hypothetical strategy).

These ICE strategies are also summarized in tabular form in Section [6.14](#).

Handling Rules for Missing Continuous Data for Adjusted Composite Estimand

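### For clinical by-visit endpoints, ICE 5 is a share of all doses since Week 0, so one early miss drops the next visit while a 48-week gap before Week 156 is not flagged

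*SAP*

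**What the plan says.** SAP 5.3.6.1 generalises the intercurrent events to all Other Efficacy endpoints and all efficacy visits. ICE 5 looks only at doses missed for disruption-related reasons (a Natural Disaster or a Major Disruption), and it is met at a visit when their number "exceeds 30% of the total protocol defined doses from Week 0 up to and including that visit". The only worked value is "For Week 20, this amounts to ≥ 2 dose missed". SAP 6.14 (Appendix 14) repeats the rule. It contains no condition on when the doses were missed and no minimum count.

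The consequence is in SAP 5.3.6.2.10: "For ICE category 5, observed data at the visit immediately subsequent to meeting the ICE will not be used"; those data are then assumed missing at random. That section describes the purpose as estimating the treatment effect as though the disruption and the events it directly caused had not occurred. A permanent stop for the same causes is ICE 4, after which all later data are set aside.

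The primary endpoint uses a fixed count instead. In SAP 5.3.4.2, ICE 5 is "defined as ≥ 2 doses of study intervention missed due to Natural Disaster or Major Disruption". SAP 5.3.5.1.2 uses the same count for the key secondary endpoint, and one of the two site-exclusion criteria for the mFAS (SAP 4.3) also turns on 2 or more doses.

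**The concern.** A fixed percentage of a growing total is a moving threshold. Early on it is so low that one missed injection counts as severe. In the q8w arm the Week 8 injection is placebo (SAP 1.2), so on the written rule a missed placebo syringe at Week 8 removes that participant's Week 12 data. Late in the extension the threshold is so high that a participant can be without drug for most of a year and still have the visit analysed as if treatment had continued.

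For clinical measures such as ACR response, HAQ-DI or PASI, both results sit badly with the hypothetical strategy. Data are discarded where the disruption had little effect on exposure, and kept where its effect was large. The early visits fall within the by-visit treatment comparisons through Week 24. The late visits feed the per-arm estimates through Week 156.

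**Working it through.** **Inputs.**
- Threshold: strictly more than 30% of protocol-defined doses from Week 0 through the visit (SAP 5.3.6.1).
- Schedule to Week 48: an injection every 4 weeks in each arm, with placebo filling the gaps in q8w. For q4w, "Participants will receive SC guselkumab 100 mg at Weeks 0, 4, 8, 12, 16, 20, 24, 28, 32, 36, 40, 44 and 48" (SAP 1.2).
- Extension: "Study intervention will be administered SC q4w through Week 156" (Protocol, Table 2 footnote i).

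**Formula.** Doses scheduled from Week 0 to Week w inclusive: n = w/4 + 1. Fewest missed doses that exceed 30%: m = floor(0.3n) + 1.

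**Plan's own figure.** Week 20: n = 6, 0.3n = 1.8, m = 2. This matches the SAP. Leaving out the visit's own dose (n = 5, 0.3n = 1.5) also gives 2.

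| Week | n | 0.3n | Misses needed | Most misses not flagged |
|---|---|---|---|---|
| 4 | 2 | 0.6 | 1 | 0 |
| 8 | 3 | 0.9 | 1 | 0 |
| 12 | 4 | 1.2 | 2 | 1 |
| 20 | 6 | 1.8 | 2 | 1 |
| 24 | 7 | 2.1 | 3 | 2 |
| 48 | 13 | 3.9 | 4 | 3 |
| 96 | 25 | 7.5 | 8 | 7 |
| 144 | 37 | 11.1 | 12 | 11 |
| 156 | 40 | 12.0 | 13 | 12 |

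**Early case.** Only the Week 8 injection is missed: 1/3 = 33.3% at Week 8, so Week 12 is dropped. Only the Week 4 injection is missed: 1/2 = 50% at Week 4 and 1/3 = 33.3% at Week 8, so Weeks 8 and 12 are both dropped. At Week 12 the share is 1/4 = 25% and the same miss no longer counts.

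**Late case.** The last injection is at Week 108, so the Week 156 assessment comes 156 - 108 = 48 weeks later. The share of doses missed is:
- through Week 144: 9/37 = 24.3%;
- through Week 152: 11/39 = 28.2%;
- through Week 156, with that dose also missed: 12/40 = 30.0%, which does not exceed 30%.

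ICE 5 is not met at any of these points.

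**Boundary.** If the missed doses are Weeks 108 to 152, the share is 12/39 = 30.8% through Week 152, which meets the rule. It is 12/40 = 30.0% at Week 156 if that dose is given, which does not. Week 152 is not a scheduled extension visit.

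**q8w arm after site unblinding.** Placebo injections then leave the planned count (SAP 6.6). If they stopped straight after Week 48, n = 13 + 14 = 27 and 0.3n = 8.1, so 8 misses (29.6%) go unflagged. The last dose could then be at Week 92, 156 - 92 = 64 weeks before Week 156. This is the extreme: unblinding follows a calendar date, so n for an individual lies between 27 and 40.

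**The case against.** **A cumulative share is defensible for some endpoints.** This stands for radiographs. Their variable is change from baseline in accumulated damage, so exposure since Week 0 is relevant. Consider a participant who misses Weeks 52 to 100 (13 doses) and then resumes. The current rule flags this: 13/37 = 35.1% at Week 144 and 13/40 = 32.5% at Week 156. A rule that looked only at recent doses would not. A reader might infer that the cumulative rule also spoils the radiographic main analyses; the documents do not support that.

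**The percentage is the rule, and 2 doses is only what it gives at Week 20.** This is fair. The SAP does not state that 2 of 6 was the intent, and one miss out of two or three doses is 33% to 50% of planned treatment. But the SAP uses 2 or more doses wherever it fixes a count, and does not explain why severity should need 1 miss at Week 8 and 13 at Week 156.

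**The late case may be rare.** It needs many consecutive disruption-related misses, no permanent discontinuation and attendance at the visit. Protocol 7.1 requires discontinuation when a participant cannot keep to the visit schedule or comply with the protocol. The Major Disruption guidance allows shipment and home dosing, and SAP 4.3 and 4.4 describe temporary closures and supply interruption. A reader might infer that participants really were off drug for most of a year; nothing in the documents shows this.

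**Reach is limited.** This also stands. Other Efficacy p-values are nominal, and there are no treatment comparisons after Week 24 (SAP 5.3.6). The Ukrainian sites judged unable to support key operations are outside the mFAS. Clinical endpoints have a supportive treatment-policy analysis that excludes all Ukrainian sites.

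**A by-visit list may be missing.** The Week 20 sentence ends in a colon, so text may have been lost in extraction. Appendix 14 restates the complete rule without such a list.

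**Conclusion.** The point holds for clinical (non-radiographic) by-visit endpoints. The number of missed doses that triggers ICE 5 rises from 1 to 13 over follow-up. At the early end one missed injection, possibly placebo, removes the next visit. At the late end an assessment 48 weeks after the last injection is kept as observed, contrary to the hypothetical strategy in SAP 5.3.6.2.10.

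The figures assume injections every 4 weeks, all misses due to the disruption, consecutive misses in the late case, and a participant who has not permanently discontinued. The 12-of-40 result depends on the word for strictly greater. The 48-week result does not, because 11/39 and 9/37 are also below 30%.

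It should not be read as a threat to the trial's confirmatory conclusions: the primary and key secondary analyses use the fixed count. Nor does ICE 5 void all later data, since it removes one visit each time it is met. The late effect is on descriptive or model-based per-arm summaries, and the number of participants affected is not known. It is worth correcting because the change is small and the present rule works against its stated purpose.

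**What to change.** **Clinical endpoints.** In SAP 5.3.6.1 and Appendix 14, define ICE 5 at a visit as at least 2 protocol-defined doses missed because of a Natural Disaster or Major Disruption, among those scheduled in the 24 weeks before that visit (not counting the visit's own dose). Align the action in 5.3.6.2.10 so that the data set aside are those of that visit.

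At Week 24 the window holds Weeks 0 to 20, six doses, so the rule reproduces the count of 2 or more used for the primary endpoint. A single early miss no longer removes a visit, and the Week 108 example is flagged at Week 156. State the window in calendar time, so that it covers the same period in both arms once q8w placebo injections stop. Six scheduled doses would then span about 48 weeks in q8w against 24 in q4w. One asymmetry remains: without placebo, a 24-week window holds three q8w doses, so 2 misses are a larger share there.

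**Radiographic change-from-baseline endpoints.** Keep the cumulative rule, but require at least 2 missed doses.

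**Cost.** SAP wording and one revised derivation. Some late off-drug clinical data would be set aside and modelled under MAR. For any database lock already analysed, run the new rule as a supportive analysis. Tabulating by arm and visit how many participants change status would show whether the issue matters in practice.
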